1.0 GOALS AND OBJECTIVES (SCIENTIFIC AIMS)

In patients with relapsed or relapsed/refractory multiple myeloma (MM):

Phase I

Primary Objectives:

- To determine the maximum tolerated dose (MTD) and recommended phase II dose (RP2D) of leflunomide, when given as a single agent.
- To assess the safety and tolerability of leflunomide at each dose level by evaluation of toxicities including: type, frequency, severity, attribution, time course and duration.

Phase II

Primary Objective:

- To evaluate the anti-myeloma activity of leflunomide, when given as a single agent, as assessed by overall response rate (ORR).

Secondary Objectives:

- To obtain estimates of:
 - Response duration
 - Clinical benefit response
 - Overall survival and
 - Progression-free survival.

Clinical Pharmacology Objectives (Phase I and II)

- To characterize the relationship between serum concentration of the active leflunomide metabolite, teriflunomide (A77 1726), and toxicity.
- To assess the relationship between serum concentration of the active leflunomide metabolite, teriflunomide A77 1726), and disease response.

Exploratory Ex-Vivo and Molecular Objectives (Phase I and II)

- To explore the relationship between polymorphisms in the *CYP1A2*, *CYP2C19*, or *DHODH* genes and toxicity/response. *CYP1A2*, *CYP2C19* are the hepatic enzymes responsible for leflunomide metabolism.
- To explore the *ex vivo* cytotoxicity of leflunomide toward primary MM cells, in order to evaluate whether individual *ex vivo* leflunomide response might be a useful predictor of therapeutic response.
- To explore the potential additive or synergistic effects of combining leflunomide with other classes of FDA-approved drugs. The classes include HDAC inhibitors, immunomodulatory drugs [IMiDs], proteasome inhibitors, steroid hormones, and antibody therapeutics such as the CD38 antibody daratumumab.
- To generate a preliminary RNA/miRNA and DNA methylation signature associated with response of MM cells to leflunomide *in vivo* (mRNA/miRNA and DNA methylation, phase II only) and teriflunomide *ex vivo* (mRNA/miRNA).

2.0 BACKGROUND

2.1 Introduction/Rationale for Development

Multiple myeloma (MM) is a plasma cell malignancy characterized by periods of remissions and relapses. Worldwide, the incidence of MM is about 86,000 cases annually with about 63,000 deaths each year [4]. In the United States, over 30,000 patients are expected to be diagnosed with MM in 2016 and more than 12,000 patients will die from the disease [5, 6].

Treatments for MM include alkylating agents, immunomodulatory (IMiD) drugs, proteasome inhibitors, anthracyclines, and glucocorticoids. Therapeutic agents are used sequentially or in combination either as double, triple or quadruple chemotherapy combinations. While the prognosis for MM patients has improved [7, 8], MM remains an incurable disease with a median survival of approximately 3 to 4 years with standard therapy[9]. The 5-year survival rate for patients with MM is estimated at 46% (Cancer Statistics 2016), with only 17% of patients surviving for 10 years[10].

Relapsed and refractory multiple myeloma (RRMM) is defined as disease that is nonresponsive while on salvage therapy, or progressing within 60 days of cessation of the most recent prior therapy in patients who have achieved minimal response (MR) or better[11]. Primary refractory myeloma is defined as disease that is nonresponsive in patients who have never achieved a minimal response or better with any therapy[11]. The overall survival for patients who have received more than 3 prior regimens and whose disease has relapsed after treatment with bortezomib and lenalidomide is estimated to be between 6 and 10 months [12, 13]. Treatment decision making in the RRMM population is particularly challenging, given underlying comorbidities and the toxic nature of available agents. Moreover, duration of response to therapies is traditionally short due to multi-drug resistance as well as changes in disease biology (e.g., development of aggressive phenotype, higher proliferation rates, and lower apoptotic rates) [14]. Patients with RRMM are in dire need of new treatments with new mechanisms of action that could be used successfully long term.

2.2 Leflunomide

Leflunomide is a commercially available oral immunosuppressive agent that has been FDA approved since 1998 for the treatment of rheumatoid arthritis (RA) as a single agent or in combination with methotrexate. It has been used in over 300,000 patients worldwide for RA treatment. Leflunomide is generally well-tolerated and may be taken over a long period of time.

The in vitro and in vivo mechanisms of leflunomide are not completely defined. The primary clinical mechanism of action is inhibiting de novo pyrimidine synthesis by targeting dihydroorotate dehydrogenase (DHODH), and thus achieving anti-proliferative effect in B- and T-lymphocytes. A secondary mechanism of action is inhibition of cytokine and growth factor receptor associated tyrosine kinase activity [15].

Leflunomide (the pro-drug) is rapidly converted to its active primary metabolite teriflunomide (A77 1726), which mediates leflunomide's pharmacologic activity. Teriflunomide serum concentrations show wide inter-patient variability; in one study, the mean serum teriflunomide concentration in patients receiving 20 mg/ daily was 42 mg/l with a range from 3-150 mg/l and a standard deviation of 35 mg/l [16]. Of note, the serum concentration of this metabolite was shown to predict RA response[16].

The FDA approved dose in adults for the treatment of RA is a loading dose of 100 mg orally (PO) once daily for 3 days, followed by a maintenance dose of 10-20 mg PO once daily. Leflunomide has been used at up to 40 mg/day in patients with Wegner's granulomatosis with a safety profile similar to the 20mg/day dose used in RA [17, 18]. Doses up to 60 mg/day have been safely used for the treatment of allograft polyoma BK virus in renal allograft patients to achieve a targeted blood level of teriflunomide

(A77 1726) of 50-100 micrograms/mL [19]; the targeted blood level was frequently achieved with a dose of 40mg/ day with no increase in toxicity reported [19].

In addition to studies that demonstrate the serum concentration of the metabolite may predict response, recent work demonstrates that polymorphisms in the gene encoding DHODH may be associated with leflunomide treatment outcome in RA patients[20, 21].

The long half-life of the metabolite (about 2 weeks) affects management of patients taking leflunomide. A loading dose of 100 mg for 3 days is used to facilitate rapid attainment of steady state levels of M1. Without a loading dose, it is estimated that attainment of steady state concentrations would require nearly two months of dosing [22]. To eliminate the metabolite, a drug elimination procedure using cholestyramine is recommended. Cholestyramine, a bile acid sequestrant, fixes the metabolite, preventing reabsorption and expediting drug elimination. Without the drug elimination procedure, it may take up to 2 years to reach non-detectable plasma levels after stopping treatment with leflunomide [22].

2.5 Background for Correlative Studies

Leflunomide is rapidly converted to its active primary metabolite teriflunomide (A77 1726), which mediates leflunomide's pharmacologic activity. Previous population-based PK studies in patients with RA have demonstrated a high degree of intersubject variability in measured steady-state total (free + albumin-bound) teriflunomide serum concentrations, resulting in coefficients of variation in CL/F estimates of >50% [29, 30]. Teriflunomide is >99% bound to serum albumin and free drug concentrations have also been reported to be highly variable, with a median of 55.8 µg/l and a range of 27.9-148.4 µg/l [31]. Moreover, measured total and free teriflunomide levels have been shown to predict response and toxicity in RA patients, leading some investigators to suggest a role for therapeutic drug monitoring and dose optimization of leflunomide [16]. It has also been reported that genetic polymorphisms in CYP1A2 and CYP2C19, the hepatic enzymes responsible for leflunomide metabolism, and DHODH, a key enzyme in the *de novo* synthesis of pyrimidines and the main target of teriflunomide, can all influence the risk of leflunomide-associated toxicity in RA patients [32-34]. DHODH is expressed in MM cells, however, the relationship between DHODH gene polymorphism and toxicity/response to leflunomide is not well understood. Therefore, a better understanding of the relationship between teriflunomide serum concentrations and toxicity/response, as well as the influence of inherited polymorphisms in the genes involved in the metabolism and mechanism of action of leflunomide is needed.

Various distinct genomic and epigenomic abnormalities have been observed in multiple myeloma, including gene mutations, chromosomal abnormalities, and DNA methylation [35]. Inhibition of tumor suppressor gene expression by DNA hypermethylation promotes survival and expansion of MM cells and clinical outcomes have been recently linked to DNA methylation status of MM cells [36]. Molecular signatures capturing such gene expression data have also recently emerged as powerful tools to identify patients who might respond particularly well to a specific treatment. Although genomic and epigenomic markers show promise for MM, there are still very few studies available and reliable markers have not yet emerged.

2.6 Overview and Rationale of Proposed Study

The pre-clinical data, along with limited although promising clinical data of leflunomide for treatment MM, and the relatively low toxicity profile seen with prolonged administration in the rheumatoid arthritis population, in total provide evidence to support the investigation of leflunomide as an anti-myeloma agent. This single agent phase I/II dose-escalation trial is designed to determine the MTD and to generate information about efficacy at the RP2D. Relapsed or relapsed/refractory multiple myeloma (RRMM) patients with documented measurable disease after at least three prior regimens will be considered for enrollment.

While the standard dose of leflunomide (20mg daily), following a loading dose of 100mg daily for 3 days, is FDA approved for continuous treatment of rheumatoid arthritis, leflunomide has been administered without an increase in the type, frequency or severity of adverse events at doses up to 40 mg/day in patients with Wegner's granulomatosis, and up to 60mg/day in a subset of patients with polyoma BK neuropathy to achieve targeted therapeutic levels [17, 18].

Because the current dosing guideline for patients with rheumatoid arthritis do not to exceed 20 mg daily maintenance doses [22], the 20mg/day dose is selected as the safe starting dose. We will attempt to escalate the dose of leflunomide to three times that approved for RA using a modified rolling six dose-escalation/ de-escalation/expansion design, a more conservative version of the rolling six design of Skolnik, et al.[1]. The starting dose of leflunomide is 20mg daily, with the intention to test up to 60mg daily. Escalation will proceed in increments of 20mg/day (odd numbered dose levels); de-escalation will proceed in decrements of 10mg/day.

Patients will be treated in planned 28-day treatment cycles. Patients may continue to receive cycles of treatment on study until disease progression or unacceptable toxicity, or other criteria for removal from study treatment are satisfied. While on active treatment patients will undergo monthly evaluation for response using the International Myeloma Working Group (IMWG) criteria [37, 38]. Following the decision to end leflunomide treatment, all patients will undergo 11 days of treatment with cholestyramine, which fixes the metabolite, preventing re-absorption and effectively lowering drug levels. Cholestyramine has been shown to decrease plasma levels of teriflunomide (A77 1726) in healthy volunteers by approximately 40% in 24 hours and by 49-65% in 48 hours [22].

Previous RA studies have shown a large variation in the serum concentration of the primary active metabolite, teriflunomide (A77 1726), and a suggested association between serum concentration of this metabolite and response [19]. Although the prior PK/PD relationship was identified in a non-oncologic patient population, it is possible that a similar association could exist for leflunomide exposures and antitumor response. Therefore, as part of the secondary objectives for this trial, enrolled RRMM patients will have blood samples collected and then processed by the Analytical Pharmacology Core Facility (APCF) to assess the possible relationship between serum concentration of the active leflunomide metabolite (teriflunomide) and toxicity/response. The natural PK variability of leflunomide administered at fixed doses will allow us to assess patients over a wide range of measured drug exposures. If a therapeutic window for leflunomide exposure can be identified, future studies based on targeted drug exposures will be considered. Additional testing will be done on collected blood samples to assess, in an exploratory manner, the potential association between germline polymorphisms in the *CYP1A2*, *CYP2C19*, and *DHODH* gene and either toxicity or response.

In addition to the PK/PD analysis, additional molecular correlates and *ex vivo* responses will be evaluated using bone marrow specimens, which will be collected from patients before treatment and after one month of leflunomide treatment. MM cells will be purified from the pre-treatment specimens and treated with teriflunomide to determine the *ex vivo* IC50. The goal of this study is to determine whether *ex vivo* drug response predicts *in vivo* therapeutic response. The *ex vivo* treatment concentrations will be similar to *in vivo* drug levels. Teriflunomide will also be combined with drugs from other classes (e.g., HDAC inhibitors, immunomodulatory drugs [IMiDs], proteasome inhibitors, steroid hormones, and antibody therapeutics such as the CD38 antibody daratumumab), in order to evaluate *ex vivo* synergy and potentially predict the success of combination therapies. Molecular correlate analysis of leflunomide response will include miRNA, mRNA and DNA methylation profiling. Specimens derived from before and after leflunomide treatment (after 1 month and at progression or complete response, if possible) will be analyzed, as well as pre-treatment specimens exposed to teriflunomide *ex vivo*. The miRNA, mRNA and DNA methylation profiling analysis of specimens derived from participants treated with leflunomide *in vivo* will be conducted only for participants treated at the RP2D in order to minimize extra interventions for participants who may not receive a therapeutically effective dose.

Following completion of the phase I portion of the study and identification of the RP2D, the phase II portion of the study will be initiated. Recent studies evaluating daratumumab, a CD38 monoclonal antibody, as monotherapy for relapsed/refractory multiple myeloma were recently published [39, 40] and have led to FDA approval of this agent. One study included patients with relapsed multiple myeloma treated with at least three lines of therapy while the other included patients treated with at least two prior lines of treatment. Treatment with daratumumab as a single agent lead to an overall response rate of 29.2% and 36% respectively in each of these studies. In both studies, the agent investigated was well tolerated but required IV dosing once weekly for 8 doses, followed by twice-monthly doses for 8 doses and then monthly thereafter. We suspect leflunomide to be similarly well tolerated but with a more convenient dosing schedule. Because we are including patients who have received at least three prior lines of treatment, we will target an overall response rate of 30% for the phase II portion of the study.

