
Analysis: Observed toxicities will be summarized in terms of type (organ affected or laboratory determination), severity, attribution, time of onset, duration, serum concentration of the active leflunomide metabolite, probable association with the study treatment and reversibility or outcome. Baseline information (e.g. the extent/type of prior therapy) and demographic information will be presented as well to describe the patients treated in this study.
 
Rates and 95% Clopper Pearson binomial confidence interval (CI) will be calculated for overall response rate (patients that have confirmed sCR/CR/VGPR or PR) and clinical benefit rate (patients that have confirmed sCR/CR/VGPR/PR/MR or SD). In addition, sub-analyses will be performed where participants will be considered evaluable for response if they are confirmed eligible, receive at least 75% of leflunomide during the first cycle of therapy and have their disease re-evaluated. Response rates will also be explored based on number/type of prior therapy(ies) and serum concentration of the leflunomide metabolite (μg/mL). Time to response and survival will be estimated using the product-limit method of Kaplan and Meier.
 
Serum trough levels of leflunomide's active metabolite, teriflunomide (A77 1726), will be measured in each patient at multiple time points throughout the study. Both total and free teriflunomide will be tested. The association between serum levels and toxicity, as well as response, will be evaluated at the conclusion of the study.
 
Genetic polymorphisms in genes associated with the biological activity of leflunomide (e.g., DHODH, CYP1A2, and CYP2C19) have been previously described and will be explored for possible associations with response and safety outcomes.
 
Ex vivo studies will be performed on bone marrow aspirate-derived cells to evaluate the IC50 for teriflunomide and the potential synergy with other anti-neoplastic agents. Correlation analyses will be performed to determine the relationship between ex vivo and in vivo response.
 
Preliminary molecular profiles for miRNA, mRNA, and DNA methylation status will be derived from both ex vivo and in vivo treatment. These profiles will be used to identify molecular correlates of therapeutic response using pathway identification and supervised principal components analysis.

Sponsor/Licensee:
Investigator Initiated: City of Hope
Case Report Forms

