Pharmacokinetics: Because serum concentration of the metabolite, teriflunomide (A77 1726), can be variable, and because some studies have found an association between serum concentration of this metabolite and RA response, samples will be collected throughout the study for analysis by the Analytical Pharmacology Core Facility (APCF) for an exploratory analysis relating metabolite levels to safety and efficacy outcomes. At the conclusion of the study, total and free teriflunomide levels will be summarized at 2- and 4-week sampling time points. Descriptive statistics will be used to characterize possible inter-patient variability and relationship to dose, toxicity and response for future studies, including guidance with respect to RP2D selection. Additional testing and analysis will be done on collected samples to assess, in an exploratory manner, the potential association between germline polymorphisms in the DHODH gene and either toxicity or response.

Pharmacogenomics: To evaluate the independent effect of germline polymorphisms, all models will be adjusted for risk factors known to be associated with outcomes studied (e.g., age, disease status). Multiple comparisons adjustment with false discovery rate (FDR) will be conducted, and variants with $FDR \leq 0.05$ will be considered significant. We will specifically look at *DHODH*, *CYP1A2* and *CYP2C19* gene polymorphisms and haplotypes identified in the literature that are associated with leflunomide response/toxicity in RA. Functional annotation of the variants will be performed using ANNOVAR. The major goal of this analysis is to identify potential SNPs that might affect the responsiveness of treatment, other than the miRNA/mRNA/methylation signature. Given the small sample size, we consider this analysis as exploratory and may not provide enough power to detect significant associations.

***Ex vivo* and molecular studies:** The IC50 values for teriflunomide in MM cells will be calculated using Prism software (GraphPad). These values will be used for correlation analysis to determine the strength and linearity of the relationship between the *ex vivo* response and the response characteristics *in vivo*. The results will also be compared to responses from cell lines.

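### The exploratory IC50-response analysis leaves out each patient's measured teriflunomide level, which costs some power and makes a null result hard to interpret

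*Combined protocol and SAP*

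**What the plan says.** Section 2.6 gives the purpose of the ex vivo testing: "The goal of this study is to determine whether *ex vivo* drug response predicts *in vivo* therapeutic response". Sections 1.0 and 2.6 make clear that the IC50 comes from pre-treatment cells and is wanted as a possible predictor. The objective is listed as exploratory.

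The synopsis describes the analysis in one sentence: "Correlation analyses will be performed to determine the relationship between" the ex vivo and in vivo responses. Section 13.5 says of the IC50 values: "These values will be used for correlation analysis to determine the strength and linearity of the relationship between the *ex vivo* response" and the in vivo response characteristics. Neither place names drug level or dose.

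On exposure, Section 2.2 reports that the mean level at 20 mg daily in one earlier study "was 42 mg/l with a range from 3-150 mg/l and a standard deviation of 35 mg/l". Section 2.5 adds variability from population studies, "resulting in coefficients of variation in CL/F estimates of >50" per cent. Section 2.6 treats this spread as useful, because it "will allow us to assess patients over a wide range of measured drug exposures". Sections 9.1 to 9.1.4 provide for total and free troughs in all participants. Section 13.5 relates these levels to toxicity and response, but separately from IC50.

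Table 9.3.2 shows that cytotoxicity is tested in both phases, so phase I patients at doses other than the RP2D also enter.

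**The concern.** An IC50 is a concentration. Whether a patient's cells are inhibited depends on the level reached relative to it. Two patients with the same IC50 can have different outcomes because one absorbs or clears the drug differently. If exposure drives response, which Section 2.6 itself considers possible, an analysis of IC50 alone carries that variation as unexplained noise.

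At stake is how the result is read. A weak or absent correlation could mean that the assay does not predict response, or that drug levels differed too much for the prediction to show. The plan has the data to help tell these apart but does not bring them together.

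**Working it through.** **The plan's own figures.** No sample size or power is stated for the IC50 analysis, so there is none to reproduce. The patient number comes from the Simon design in Section 13.3: 19 then 39 patients, continuing on 4 or more responses and succeeding on 9 or more. The exact binomial calculation gives early stopping probability 0.684 at a 15% response rate (stated 0.68), type I error 0.097 (limit 0.10) and power 0.803 at 30% (stated 80%). The design reproduces.

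**Patients and doses.** Section 13.4 expects 3 patients at 20 mg, 3 at 40 mg and 6 at 60 mg in phase I. Section 5.4 counts the 6 at the RP2D towards the 39. The total is 39 + 6 = 45, of whom 39 share one dose.

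**Exposure spread (Section 2.2: mean 42, SD 35, range 3-150 mg/L).**
- Minimum to maximum: 150/3 = 50-fold.
- CV = 35/42 = 0.83.
- If lognormal, log-SD = sqrt(ln(1 + 0.83²)) = 0.726.
- Central 95%: exp(2 × 1.96 × 0.726) = about 17-fold.
- For comparison, the free-drug range in Section 2.5 is 148.4/27.9 = 5.3-fold.

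**What omission does to the association.** Assume a latent response = log C − log IC50 + normal noise, with C independent of IC50 and half the variance explained. The total variance is then 2 × (0.726² + s²), where s is the log-IC50 SD. The documents do not give s. The values 0.35 and 0.7 are assumptions; they put ±2 SD at exp(4 × 0.35) = about 4-fold and exp(4 × 0.7) = about 16-fold.
- s = 0.35: total variance = 2 × (0.527 + 0.1225) = 1.30. The IC50 share is 0.1225/1.30 = 0.09, so r = 0.31. With exposure removed it is 0.1225/(1.30 − 0.527) = 0.16, so r = 0.40.
- s = 0.7: total variance = 2 × (0.527 + 0.49) = 2.03. The IC50 share is 0.49/2.03 = 0.24 (r = 0.49), against 0.49/(2.03 − 0.527) = 0.33 (r = 0.57).

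**Power by simulation.** n = 39, response rate 30%, two-sided 5% likelihood-ratio test in both columns:

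| Exposure | log-IC50 SD | IC50 alone | Adjusted for log C | Gain |
|---|---|---|---|---|
| log-SD 0.726 | 0.35 | 0.32 | 0.44 | 0.12 |
| log-SD 0.726 | 0.7 | 0.70 | 0.78 | 0.08 |
| CV 50% | 0.35 | 0.57 | 0.67 | 0.10 |

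Using one test throughout matters. A rank test for IC50 alone set against a likelihood-ratio test for the adjusted model would overstate the gain.

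**Sensitivity to the model.** A logistic model was run over 54 scenarios: response rate 15% or 30%; 19, 39 or 45 patients; log-IC50 SD 0.35, 0.7 or 1.0; slope 1, 2 or 4. The gain ranged from about 0 to 29 points, largest when IC50 varied little and the slope was steep. Power for IC50 alone ranged from 0.10 to about 1.00. It was below 50% in 29 scenarios, and adjustment lifted only 6 of those to 50% or more.

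**If the outcome is graded rather than yes/no.** Use power = Φ(atanh(r) × sqrt(n − 3) − 1.96), with one fewer patient for the adjusted analysis. For s = 0.35, residual SD 0.7 gives 0.53 alone and 0.81 adjusted; residual SD 1.0 gives 0.39 and 0.53. For s = 0.7 and residual SD 1.0 the figures are 0.90 and 0.97. The direction is the same.

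**The case against.** The strongest argument is that the protocol asks about a pre-treatment predictor. A trough drawn during treatment is unknown when the prediction would be used, so IC50 alone answers that question directly. This stands: the exposure-adjusted model belongs beside the planned correlation and should not replace it.

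A reader might infer that a real IC50 effect is likely to be missed because exposure is left out. The documents do not support this. They give no between-patient IC50 spread and no effect size. The 50-200 µmol/L in Section 2.3 describes concentrations active in cell lines, not a distribution of patient IC50s. Where power is low, the usual cause is few patients and responders; in the first row of the table it stays below 50% even after adjustment.

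A reader might also take 50-fold as the working spread. That is the minimum-to-maximum of total drug in one earlier study; 17-fold is the fairer summary, and free drug may vary less. Nor is dose mixing a large part of the problem, with about 39 of 45 patients expected at one dose.

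Finally, the aim is exploratory, carries no power claim and drives no decision. Section 13.5 also speaks of linearity, so the outcome may be graded and the binary simulation may not match the analysis intended. Both points limit the importance of the finding, but neither supplies the missing joint analysis.

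**Conclusion.** The point holds in a limited form. The planned IC50 analysis ignores a measured quantity that the protocol's own figures show to vary widely at one dose. Under the stated assumptions (39 complete pairs, 30% response, lognormal exposure independent of IC50, half the latent variance explained, log-IC50 SD 0.35 to 0.7) this costs roughly 8 to 12 points of power. Other assumed values give about 0 to 29 points. With exposure independent of baseline IC50, the omission adds noise and creates no false association. The practical consequence is that a null result would be ambiguous. Adjustment reduces that ambiguity but does not overcome the small sample.

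**What to change.** In Section 13.5, keep the IC50-only correlation as the answer to the pre-treatment predictor objective. Add a prespecified exploratory model of in vivo response on log IC50 adjusted for log trough, and also report log(trough/IC50) as a single predictor. Specify in advance:

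- **One IC50.** Appendix B yields values at 24, 48 and 72 hours, by ATP and by Annexin V; the 72-hour ATP value is one candidate.
- **Total or free trough.**
- **One early trough already scheduled.** Use cycle 2 day 1, or the cycle 1 day 14 sample for patients who stop earlier, so that early non-responders are not dropped. Flag which sample was used.
- **The in vivo response measure**, binary or graded.

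The cost is SAP wording and a little analysis time, with no new samples. The downsides are one extra parameter in a small model and some troughs that may still be missing; the number of patients with complete pairs should be reported.
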